### Time to freedom from mechanical ventilation

This will be measured in hours and will be derived as:

(date/time of extubation – date/time of ICU admission)/3600. The result will be rounded to the nearest integer.

#### Duration of ICU stay

This is the interval in hours between ICU admission and ICU discharge and will be derived as: (date/time of ICU discharge – date/time of ICU admission)/3600. The result will be rounded to the nearest integer.

#### PGD Score

This is graded as an integer between 0 and 3 according to the following definitions:

Grade 0	no radiographic infiltrates
Grade 1	$\text{PaO}_2/\text{FiO}_2 \geq 300$ mmHg + radiographic infiltrates consistent with pulmonary oedema
Grade 2	$200 \text{ mmHg} \leq \text{PaO}_2/\text{FiO}_2 < 300$ mmHg + radiographic infiltrates consistent with pulmonary oedema
Grade 3	$\text{PaO}_2/\text{FiO}_2 < 200$ mmHg + radiographic infiltrates consistent with pulmonary oedema

#### Duration of study drug infusion

This is measured in hours and derived as follows:

(date/time of termination of infusion – date/time of start of infusion)/3600.

The duration should be adjusted for documented interruptions of at least one hour or cumulative interruptions of at least 2 hours. The CRF does not provide a place to record interruptions so the clock times of infusion interruptions and infusion re-start will be provided via filenotes where applicable.

#### Amount of study drug infused

This is measured in milliliters and will be derived as the sum of each of the dosing intervals multiplied by the relevant infusion rate. Assuming that dosing is performed per protocol, the formula will be:

$$\begin{aligned} & (\text{date/time of dose switch} - \text{date/time of start of infusion})/3600 \times \text{infusion rate for loading dose} \\ & + \\ & (\text{date/time of bag switch} - \text{date/time of dose switch})/3600 \times \text{infusion rate for maintenance dose} \\ & + \\ & (\text{date/time of end of infusion} - \text{date/time of bag switch})/3600 \times \text{infusion rate for bag 2.} \end{aligned}$$

If the dose switch is not performed then it will be:

$$\begin{aligned} & (\text{date/time of bag switch} - \text{date/time of start of infusion})/3600 \times \text{infusion rate for loading dose} \\ & + \\ & (\text{date/time of end of infusion} - \text{date/time of bag switch})/3600 \times \text{infusion rate for bag 2.} \end{aligned}$$

If the bag switch is not performed then it will be:

$$\begin{aligned} & \text{date/time of dose switch} - \text{date/time of start of infusion})/3600 \times \text{infusion rate for loading dose} \\ & + \\ & (\text{date/time of end of infusion} - \text{date/time of dose switch})/3600 \times \text{infusion rate for maintenance dose.} \end{aligned}$$

If neither the dose switch nor the bag switch are performed then the formula will be:

$$(\text{date/time of end of infusion} - \text{date/time of start of infusion})/3600 \times \text{infusion rate for loading dose.}$$

For repertaxin, the amount of study drug in milligrams will be derived as  $12.65 \times$  total volume transfused in milliliters.

#### Treatment-emergent adverse events

Treatment-emergent adverse events are those which first occur or increase in severity after the first dose of study drug. Adverse events with a start date greater than or equal to the start date of study drug infusion will be considered to be treatment emergent. If the onset date is missing then the event will be assumed to be treatment-emergent. If the start date is partial and only the month and year are populated then all events starting in the same month as the study drug infusion will be assumed to be treatment-emergent. If the start date is partial and only the year is populated then all events starting in the same year as the study drug infusion will be assumed to be treatment-emergent.

#### Systemic Vascular Resistance (SVR)

This is measured in  $\text{dyn}\cdot\text{s}\cdot\text{cm}^{-5}$  and is derived as:

$$80 \times (\text{MAP} - \text{CVP})/\text{CO} \text{ where MAP} = \text{mean arterial pressure} = \text{DBP} + (\text{SBP} - \text{DBP})/3.$$

#### Pulmonary Vascular Resistance (PVR)

This is measured in  $\text{dyn}\cdot\text{s}\cdot\text{cm}^{-5}$  and is derived as:

$$80 \times (\text{MPAP} - \text{PCWP})/\text{CO}$$

where MPAP = mean pulmonary arterial pressure

$$= \text{systolic PA pressure} + (2 \times \text{diastolic PA pressure})/3.$$

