7.5. ADMISSION TO ICU

7.5.1. Arrival to the ICU

Date and time of ICU admission will be recorded in the CRF.

All patients will be mechanically ventilated through a oral endotracheal tube. The ventilator mode and rate will be set as per center practice, to ensure best standard of patient care.

Upon arrival to the ICU, the patient will be hemodynamically stabilized and placed on $FiO_2 = 1.0$ and $PEEP = 5$ cmH₂O (or greater, if clinically necessary, to achieve $SpO_2 > 92\%$ and $PaO_2 \geq 75$ mmHg).

The following will be assessed as per center practice (unless otherwise specified) on arrival to the ICU and recorded in the CRF, apart from SVR and PVR which will be calculated during data-management:

- PaO_2/FiO_2 ratio ($FiO_2 = 1$; $PEEP = 5$).
- Chest X-rays (see Appendix 1 for methodological details).
- BP, HR.
- CO, PA pressure, SVR, PVR, PCWP, CVP.

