##### Cardiopulmonary measurements

Cardiopulmonary measurements consist of CVP, PCWP, CO and PA Pressure (systolic/diastolic) and are measured at ICU admission, every 12 hours post ICU admission until 120 hours post ICU admission or until ICU discharge or PA catheter removed whichever occurs earliest. These data will be summarized by treatment group at each time point. Summary statistics for the derived variables SVR and PVR (see Section 5 for definitions) will also be provided.

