## 10 VALIDATION

All summary tables and figures will be validated by independent programming within SAS. Any numerical discrepancies will be resolved prior to finalization of the tables and figures. All outputs will have the following checks performed:

- Titles and footnotes are correct
- No errors or warnings in SAS log file
- Expected number of observations in dataset used for final output
- Matches the specifications documented in this plan

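### The SAP formula for mean pulmonary artery pressure divides only the diastolic term by 3, so the mean exceeds systolic pressure and PVR is overstated, about threefold at ordinary pressures

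*SAP*

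**What the plan says.** In SAP Section 5, the PVR entry gives PVR in dyn·s·cm⁻⁵ as 80 × (MPAP − PCWP)/CO, "where MPAP = mean pulmonary arterial pressure". The next line sets MPAP equal to systolic PA pressure plus a bracket holding twice the diastolic PA pressure, with the division by 3 applied to that bracket alone. In the extracted text, with its typesetting markup, it reads "systolic PA pressure} + (2 \times \text{diastolic PA pressure})/3".

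The entry immediately before it, for systemic vascular resistance, defines mean arterial pressure as DBP + (SBP − DBP)/3.

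Four other places determine how the PVR line is used:

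- Protocol 4.2.4 lists PVR among the cardiopulmonary safety measurements, taken at ICU admission and every 12 hours while a PA catheter is present, up to ICU discharge or 5 days.
- Protocol 7.5.1 has these measurements recorded in the CRF, "apart from SVR and PVR which will be calculated during data-management".
- SAP 9.6.6 states "Cardiopulmonary measurements consist of CVP, PCWP, CO and PA Pressure (systolic/diastolic"), so no mean PA pressure is listed as a recorded item. It continues: "Summary statistics for the derived variables SVR and PVR (see Section 5 for definitions) will also be provided".
- SAP Section 10 relies on independent programming and a list of output checks, one of which is "Matches the specifications documented in this plan".

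**The concern.** A mean pressure must lie between diastolic and systolic. The SAP's expression gives a value above systolic, so it cannot be a mean. Because PVR is not measured at the bedside, this definition is its only source, and neither document gives another formula for mean PA pressure.

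A programmer who follows the SAP exactly produces wrong values. A second programmer who does the same agrees with the first, so double programming does not expose the fault.

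The summary of PVR by treatment group would then be too high throughout. Since the error depends on each patient's systolic pressure and cardiac output, it is not a constant that drops out of comparisons between arms or over time.

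**Working it through.** The documents state no PVR, MPAP or PA pressure value, so there is no figure in the plan to reproduce. The check is algebra, followed by illustrative numbers.

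**Inputs from SAP Section 5**

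- PVR = 80 × (MPAP − PCWP)/CO
- MPAP as written: S + 2D/3
- Mean as formed for SVR: DBP + (SBP − DBP)/3 = (SBP + 2 × DBP)/3. The pulmonary equivalent is (S + 2D)/3.

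**Algebra, true for any patient**

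- Written MPAP − S = 2D/3, which is above zero whenever D > 0. The written mean therefore exceeds systolic pressure.
- Written MPAP − correct MPAP = S + 2D/3 − (S + 2D)/3 = 2S/3.
- Error in PVR = 80 × (2S/3)/CO.
- Ratio of written to correct PVR = 1 + (2S/3)/(correct MPAP − PCWP). Cardiac output cancels.

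**Illustrative values** (assumed pressures in mmHg; CO assumed to be 5 L/min)

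| PA S/D | PCWP | MPAP correct | MPAP as written | PVR correct | PVR as written | Ratio |
|---|---|---|---|---|---|---|
| 30/12 | 10 | 18.0 | 38.0 | 128 | 448 | 3.5 |
| 35/15 | 10 | 21.7 | 45.0 | 187 | 560 | 3.0 |
| 40/20 | 12 | 26.7 | 53.3 | 235 | 661 | 2.8 |
| 80/40 | 12 | 53.3 | 106.7 | 661 | 1515 | 2.3 |
| 30/15 | 15 | 20.0 | 40.0 | 80 | 400 | 5.0 |

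First row in full:

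- Correct: (30 + 24)/3 = 18, and 80 × (18 − 10)/5 = 128.
- As written: 30 + 24/3 = 38, and 80 × (38 − 10)/5 = 448.
- Difference: 320 = 80 × 20/5, where 20 is two thirds of 30.

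**Range.** The ratio was evaluated for S from 20 to 80 in steps of 5, D/S of 0.40, 0.45 or 0.50, and PCWP of 5, 8, 10, 12 or 15, keeping cases with D at or above PCWP. It ran from 2.1 to 5.0, with median 2.5. It is lowest at high PA pressure and highest when PCWP is close to the mean PA pressure.

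**Effect on comparisons.** Take two patients with CO 5, one at 25/10 with PCWP 10 and one at 30/15 with PCWP 15. The correct PVR is 80 in both. The SAP formula gives 347 and 400, a spurious difference of 53 = 80 × (2/3) × (30 − 25)/5.

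**The case against.** The best case on the other side is that the consequence is small and recoverable.

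- PVR is only summarised descriptively (Protocol 9.4.6, SAP 9.6.6). No test, threshold or decision depends on it, and it exists only for patients with a PA catheter.
- SAP 3.1 does not name it among the data listed for the DMC statistician.
- Its components are recorded and summarised by arm, so correct values can be derived at any time.
- It looks like a bracket slip that a programmer may correct without comment. The blinded listings review in SAP 8.2, which looks for values needing investigation, might also catch it.
- The threefold figure rests on assumed pressures.
- The text was converted from PDF, so a bracket could have been lost.

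Most of this limits the size of the problem without removing it. The primary endpoint, power and alpha are untouched, and the multiple should be read as an illustration with its range. It is also fair that wrong output follows only if the line is coded literally. But literal coding is what a derivation specification asks for, and the plan's check is agreement with that specification. The SAP 8.2 review may or may not notice. The brackets in the text are balanced and nothing indicates a lost one, though a glance at the source PDF would settle it.

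**Conclusion.** The formula is wrong as written. That follows from the text alone: the MPAP it yields is above systolic pressure whenever diastolic pressure is positive, overstates the mean by exactly 2S/3, and conflicts with the SAP's own SVR entry. PVR is overstated by 80 × (2S/3)/CO in every patient for whom it is calculated this way.

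The multiple depends on pressures the documents do not give. It is about 2.4 to 3.5 at ordinary assumed values and 2.1 to 5.0 over the wider assumed range. The absolute values also assume CO in L/min, which fits the factor of 80 and the stated units.

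This should be corrected, but its reach is confined to one derived, descriptive safety variable.

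**What to change.** Replace the MPAP line in SAP Section 5 with MPAP = (systolic PA pressure + 2 × diastolic PA pressure)/3, or with diastolic + (systolic − diastolic)/3 to match the form used for SVR. Then confirm that the data-management derivation and the independent validation program both use it, and check PVR wherever it is shown. Table 3.6 (cardiopulmonary measurements) is the main place. Listings 4.17.1 and 4.17.2 need checking if they carry PVR, which their titles do not say. A simple program check that derived MPAP lies between the recorded diastolic and systolic pressures would catch any recurrence.

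The cost is one moved bracket and a short program check. SAP 1.1 leaves the plan open until database lock, and SAP 1.3 already records a specification slip corrected in the same way. There is no statistical downside.

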#### BOS Score

This is an integer between 0 and 3 based on FEV1 categories defined as follows:

BOS 0	FEV 1 $\geq$ 80% of baseline value
BOS 1	FEV 1 66-80% of baseline value
BOS 2	FEV 1 51-65% of baseline value
BOS 3	FEV 1 $\leq$ 50% of baseline value

The baseline value will be defined as per center practice as the best FEV1 value following surgery.

## **6 ANALYSIS POPULATIONS**

The primary analysis of the primary efficacy variable will be presented for the intention-to-treat (ITT) population. A secondary confirmatory analysis will be performed using the per protocol (PP) population.

### 6.1 Intention-to-treat (ITT)

The ITT population will consist of all randomized patients who received any study medication and a lung transplant. Patients will be analyzed according to the treatment randomized regardless of which treatment was actually received.

### 6.2 Per protocol (PP)

The PP population will consist of all patients in the ITT population who do not meet any of the following criteria:

- Started study drug infusion after reperfusion i.e. after vascular de-clamping of the first allograft
- Received study drug infusion for less than 24 hours
- Missing data for PaO2/FiO2 ratio at both time 0 and 24 hours post ICU admission while on mechanical ventilation
- Received Orthoclone OKT3 or Campath induction immunosuppression at time of transplant. This will be recorded in the Month 1 Concomitant Medication pages if used.

Further criteria for exclusion from the PP population may be identified during the data review meeting held prior to database lock.

### 6.3 Safety

The safety population will consist of all patients who received any study medication and will be based on the treatment actually received.

## 7 INTERIM ANALYSES

No formal interim analyses of efficacy are planned for this study. However, safety data will be reviewed on an ongoing basis by a DMC. Full details of the activities and responsibilities of the DMC are provided in the study DMC charter.

## 8 DATA REVIEW

### 8.1 Data handling and Transfer

The data from this study will be entered, verified and cleaned by the Data Management group at PPD in accordance with the study data handling manual and data clarification policies. The data will be provided to the statistician as SAS datasets. The preferred term and system organ classification (SOC) from the relevant version of the MedDRA dictionary will be provided for all adverse events. The ATC group and sub-group from the relevant version of the WHO-DRUG dictionary will be provided for all prior and concomitant medications.

### 8.2 Data Review Meeting

Programming of analysis datasets, tables, figures and listings will be ongoing during the data management of the study. When the Month 1 database is considered clean by data management, a set of blinded listings (using a dummy randomization) will be produced and distributed to the study team for review. A meeting will be held to review any data values requiring investigation or correction and also protocol deviations. Once all data issues have been resolved, the Month 1 data will be locked. Treatment code unblinding and the full run of outputs will then take place.

## 9 STATISTICAL METHODS

### 9.1 General Principles

The statistical package SAS (Version 8.1) will be used to produce all summary tables, graphs and listings. In general, categorical data will be presented using counts and percentages, whilst continuous variables will be presented using the mean, standard deviation, median, minimum, maximum and number of patients. Minima and maxima will usually be reported to the same level of accuracy as the raw data; means, medians and standard deviations will be presented to one further decimal place; standard errors (if presented) will be presented to 2 decimal places more than the raw data. Percentages will be rounded to the nearest integer.

In tabulations, denominators for calculation of percentages will be taken as the number of non-missing responses in the specified analysis population and treatment group unless otherwise stated.

All data recorded in the CRF will be listed.

### 9.2 Patient Disposition

The number and percentage of patients screened, randomized and treated in the study will be presented, together with the number and percentage of patients who withdrew from the study prematurely prior to Month 1 and a breakdown of the corresponding reasons for withdrawal. The number and percentage of patients included in each of the ITT, PP and safety analysis populations will also be included. Screening data recorded for patients who do not proceed to transplant with study drug administration will be listed separately in the report. The exact format of the listings will be discussed with Dompé when the total number of patients randomized but not treated/transplanted is known.

A tabulation of the number and percentage of patients randomized at each center will be presented.

All data relating to study completion or withdrawal and inclusion in the analysis populations will also be listed.

### 9.3 Protocol deviations

Protocol deviations which exclude patients from the ITT or PP populations (see Sections 6.1 and 6.2 for definitions) will be summarized by treatment group.

### 9.4 Demographic and Baseline Characteristics

Summaries of baseline data will be produced using the safety population and will be presented by treatment group and overall. Data for parameters measured at screening that are also measured at subsequent time points post-randomization (e.g. vital signs, renal and hepatic function) will not be presented in this section. All baseline data will also be listed.

#### 9.4.1 Demographic data

Summary statistics for age (see Section 5 for definition of derivation), height and weight at screening will be presented, together with frequency counts and percentages for ethnic origin, race and gender.

#### 9.4.2 Recipient Information

Frequency counts and percentages will be presented for transplant procedure type, reasons for transplant, medical condition and CMV status. A footnote will be added to the table to clarify that multiple reasons for transplant may be indicated. Data relating to extra respiratory tract of infection will also be included. Frequency counts and percentages will be presented for blood culture results, fever and other signs of systemic sepsis syndrome.

#### 9.4.3 Significant Medical History

The total number of patients reporting any significant medical history and the total number of patients reporting significant occurrences ongoing at screening will be presented. In addition, the number and percentage of patients reporting an item of significant medical history within each of the following 15 body systems will also be presented: General Appearance; Head, Ears, Eyes, Nose and Throat; Cardiovascular; Pulmonary; Gastrointestinal; Liver; Renal; Genitourinary; Endocrine; Immune/Allergy; Psychiatric; Central Nervous System; Dermatologic; Musculoskeletal; Other.

#### 9.4.4 Donor Information

Summary statistics will be presented for the age of the donor, together with frequency counts and percentages of the gender of the donor, whether the donor was a brain dead heart beating donor and a breakdown of the reasons for brain death. If multiple reasons are provided than a footnote should be added to the table explaining that the number of reasons given will exceed the number of patients. The number and percentage of donors whose transplant organ was flushed will be presented by type of solution (Perfadex or other) and category of flush (anterograde, retrograde, additional) and the number and percentage of donors whose transplant organ was stored in either Perfadex or other solution will also be presented.

#### 9.4.5 Transplantation

The data for first and second allograft will be presented separately. For each allograft, the following data will be presented: summary statistics for the duration of cold ischemia, the duration of warm ischemia and the duration of both cold and warm ischemia (see section 5 for definitions) will be presented, together with frequency counts and percentages for the number of patients who had cardiopulmonary bypass performed. All other data relating to transplant will be listed only.

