2.4. DISEASE REVIEW AND STUDY RATIONALE

Lung transplantation has become a standard therapy for patients with end-stage lung disease. Within last decades, donor management, organ preservation, immunosuppressive regimens and control of infectious complications have been substantially improved. In addition, the operative techniques of transplantation procedures have been developed to an international standard of high quality [Lau & Patterson, 2003].

However, despite these refinements, significant reperfusion injury occurs in up to 10-20% of lung transplant recipients as the consequence of unavoidable processes of procurement, preservation and restoring blood flow. This clinical condition, recently termed primary graft dysfunction (PGD), remains an important problem after lung transplantation [Christie, 1998; King, 2000], and still represents the single biggest cause of early morbidity and mortality for lung recipients [Fischer, 2001; Thabut, 2002]. In addition, there is some evidence to suggest a relationship between reperfusion injury, acute rejection, and the subsequent development of chronic graft dysfunction [Waddell, 1996; Fiser, 2002].

Prediction of PGD is made difficult by the complexity of the interactions between the donor lung and the recipient [Sommers, 1996; McRae, 2000].

In post-ischemia reperfusion, restoration of the blood supply (reperfusion) after prolonged tissue ischemia is associated with an inflammatory reaction characterized by massive polymorphonuclear neutrophil infiltration into the reperfused tissue [de Perrot 2003]. The infiltrating inflammatory cells can perpetuate the initial inflammatory reaction and induce further injuries.

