9. STATISTICAL ISSUES

9.1. SAMPLE SIZE

The sample size has been estimated based on PaO₂/FiO₂ ratios immediately and at 24 hours from the results of 700 lung transplant operations at the Washington University. The database reports means and standard deviations for this endpoint of 329±137 mmHg at the initial ICU assessment and 315±117 mmHg at 24 hours.

A sample size of 50 in each group will have a 81% power to detect a difference in means of 70 mmHg (the difference between a placebo mean of 315 and a treated mean of 385, a 22% improvement) assuming that the common standard deviation is 137 using a two group t-test with a 0.05 one-sided significance level. Alternatively, a sample size of 50 in each group will have a 56% power to detect a difference in means of 50 mmHg (the difference between a placebo mean of 315 and a treated mean of 365, a 15% improvement) assuming that the common standard deviation is 137 using a two group t-test with a 0.05 one-sided significance level.

There is no currently available data to provide a knowledgeable estimate of the effect size in this study. If the effect size is smaller than 15%, the power of this study will be reduced and the chance of a Type II error is increased. Under such circumstances, this study would still provide valuable data regarding the effect size in the primary outcome variable as well as the results in all of the secondary, exploratory endpoints and subgroup analysis.

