### 3.2 Sample Size Considerations

Under the following assumptions:

1. A single primary endpoint –  $\text{PaO}_2/\text{FiO}_2$  ratio
2. One primary comparison: repertaxin versus placebo at 24 hours post ICU admission ( $H_0: \mu_R = \mu_P$ ;  $H_1: \mu_R > \mu_P$ ).
3. A one-sided two group t-test of statistical significance
4.  $\alpha$ -level or probability of Type I error associated with the test of 0.05
5. A placebo mean of 315 mmHg
6. A common standard deviation of 137 mmHg
7. A sample size of 50 in each group

the study has 81% power to detect a difference in means of 70 mmHg ( $\mu_R = 385$  mmHg) and 56% power to detect a difference in means of 50 mmHg ( $\mu_R = 365$  mmHg). The data for assumptions 5 and 6 is taken from the results of 700 lung transplant operations at the Washington University. However, there are currently no data available to provide an estimate of the treatment effect size for this study.

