### Duration of cold and warm ischemia

This is the interval in hours between onset of organ ischemic time and the start of reperfusion and is derived as:  
(Date/time of start of reperfusion – date/time of cross clamp on donor organ)/3600

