#### Primary analysis

The ratio at the two time points will be analyzed using a repeated measurements model using PROC MIXED within SAS®. The model will include fixed effect terms for center, time point and treatment. Time point will be specified as a repeated measurement. In order to select an appropriate matrix for the observations within each patient, 3 models will be fitted using the compound symmetry, Huynh-Feldt and unstructured structures. The matrix for the final model will be selected using Akaike's Information Criterion where the lowest value indicates the best fit. Type III sums of squares from the mixed procedure within SAS® will be used to assess the significance of individual terms within the model using the selected matrix structure. The importance of the treatment-by-center interaction will be investigated but if the term is not significant at the 10% level, it will be excluded from subsequent models. If there are insufficient data within each center and treatment combination to allow estimation of effects, centers will be pooled based on similar surgical practices.

The adjusted least squares means will be estimated for each combination of time point and treatment. The treatment effect within each time point will be compared using a one sided test at the 5% level. Missing data will be excluded. The primary analysis will be performed for the ITT population.

The tests of the fixed effects will be presented, together with the estimated least squares means and summary statistics of the raw PaO2/FiO2 ratio for each of the two treatments at each time point. The estimated treatment difference between repertaxin and placebo at each time point will be presented together with the corresponding 95% confidence interval. The confidence interval will be generated using  $\alpha=0.10$  and the lower limit will be replaced by  $-\infty$ .

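### First-allograft ischemic time is derived but only tabulated; prespecifying it as a covariate, closed before treatment can affect it, would give the primary comparison a modest, uncertain gain in precision

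*SAP*

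**What the plan says.** SAP 5 derives cold, warm and total ischemic time. The total is defined thus: "This is the interval in hours between onset of organ ischemic time and the start of reperfusion". SAP 9.4.5 then presents, separately for the first and second allograft, "summary statistics for the duration of cold ischemia, the duration of warm ischemia and the duration of both cold and warm ischemia". No listed analysis uses these values again.

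For the primary analysis, SAP 9.5.1 states: "The model will include fixed effect terms for center, time point and treatment". A treatment-by-center term stays only if it is significant at 10%. SAP 4.3 lists type of transplant as the only predetermined covariate, and it enters only a sensitivity analysis. Protocol 9.2 balances treatment within centers, and SAP 9.5.1 confirms that randomization was not stratified by type of transplant.

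Protocol 2.4 gives the biological reason for interest in ischemia: "restoration of the blood supply (reperfusion) after prolonged tissue ischemia is associated with an inflammatory reaction".

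The two documents do not close the ischemic interval at one clearly defined moment. Protocol 6.2 defines reperfusion as the return of blood flow at de-clamping of the first allograft. For patients on cardiopulmonary bypass it uses the time of coming off bypass, unless partial de-clamping came earlier. SAP 5 closes warm ischemia at the start of reperfusion or at vascular de-clamping, and closes total ischemia at the start of reperfusion only.

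**The concern.** The trial collects a measure of the insult that the drug is meant to counter, but leaves it out of the model that estimates the drug's effect. If longer ischemia goes with lower PaO2/FiO2 within a center, that variation stays in the residual and widens the confidence interval. With 50 patients per arm and a stated 56% power for 50 mmHg, precision that can be had from existing data is worth considering. Protocol 9.1 also says that no informed estimate of the effect size exists and values the trial for the estimate it will give.

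A covariate is safe only if treatment cannot alter it. Ischemic time is completed after randomization, and usually after the infusion has begun, so the choice of interval matters as much as the decision to adjust.

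**Working it through.** **Inputs.** 50 per arm, and an SD of 329±137 mmHg at ICU admission and 315±117 mmHg at 24 hours (Protocol 9.1). Effects of 70 and 50 mmHg. Test: "using a two group t-test with a 0.05 one-sided significance level" (Protocol 9.1), repeated in SAP 3.2 as "A one-sided two group t-test of statistical significance". SAP 3.2 uses SD 137 although it names the 24-hour comparison as primary. The correlation r is not stated and is assumed to lie between 0 and 0.4. Center is already in the model, so r means the correlation within centers.

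**Step 1: reproduce the plan's figures.** SE = SD × √(2/n) = 137 × √(2/50) = 27.4 mmHg. The noncentrality is 70/27.4 = 2.55 or 50/27.4 = 1.82. Power is the chance that a noncentral t on 98 df exceeds the one-sided 5% critical value.
- 70 mmHg: 81.4%. The plan says "A sample size of 50 in each group will have a 81% power to detect a difference in means of 70 mmHg".
- 50 mmHg: 56.6%. The plan says "a sample size of 50 in each group will have a 56% power to detect a difference in means of 50 mmHg".

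Both figures reproduce.

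**Step 2: add one covariate.** Residual SD = SD × √(1 − r²), on 97 df. At r = 0.3, 137 × √0.91 = 130.7. The equivalent increase in patients is 1/(1 − r²) − 1.

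| r | Power 70 / 50 mmHg, SD 137 | Power 70 / 50 mmHg, SD 117 | Equivalent extra patients |
|---|---|---|---|
| none fitted | 81.4% / 56.6% | 90.8% / 68.3% | – |
| 0 | 81.4% / 56.6% | 90.8% / 68.3% | 0% |
| 0.1 | 81.7% / 57.0% | 91.0% / 68.7% | 1% |
| 0.2 | 82.7% / 58.1% | 91.7% / 69.9% | 4% |
| 0.3 | 84.5% / 60.1% | 92.9% / 71.9% | 10% |
| 0.4 | 86.9% / 63.0% | 94.5% / 74.9% | 19% |

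Removing a second degree of freedom for a covariate-by-time-point term changes none of these by more than 0.1 point. This is the two-group calculation on which the trial was sized. It stands in for the SAP's two-time-point mixed model and does not reproduce it.

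**Step 3: is the unadjusted test wrong?** Simulated one-sided type I error (6,000 runs each, r = 0.2, 0.3, 0.4) was 4.9%, 5.0% and 4.9% without the covariate, and 5.0%, 5.0% and 4.6% with it. Both are correct within simulation error.

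**Step 4: chance imbalance.** The between-arm difference in a standardized covariate has SE √(2/50) = 0.2. At r = 0.3 and SD 137, a one-SE imbalance moves the unadjusted estimate by 0.2 × 0.3 × 137 = 8.2 mmHg. The variance splits as 27.4² × 0.09 = 67.6 from imbalance and 27.4² × 0.91 = 683.2 from the rest, which together make 27.4² = 750.8. The imbalance is therefore already inside the unadjusted SE. Adjustment removes that part and brings the SE to 26.1 mmHg.

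**Step 5: which interval is safe?** Cold ischemia ends at removal from cold storage, before the graft has met the recipient's blood. Total ischemia closed at de-clamping of the first allograft ends as drug-bearing blood first enters it. Total ischemia closed at the off-bypass time ends after the graft may already have been perfused with drug, and weaning from bypass can depend on how the graft works. The second graft's time can run on after the first has been perfused, so it can also depend on treatment.

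**The case against.** The strongest objection is that no error exists. Randomization protects the comparison, covariate choice is discretionary in a trial that SAP 9.5.1 calls not pivotal, and the benefit rests on a correlation that nobody has stated. Protocol 2.4 itself calls PGD hard to predict. Center already removes the between-center part, and in bilateral recipients first-graft time ignores the second lung, which may weaken r further. The intervals are to be tabulated by arm, so imbalance would be visible, and SAP 9.5.1 leaves room for additional robustness analyses. All of this stands as a limit on the size of the point. It does not remove it: an adjustment chosen after the arms are known is open to selection, and one fixed blind is not.

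A reader might infer two stronger claims. The first is that a chance difference in ischemic time biases the treatment estimate. Steps 3 and 4 show otherwise. The second is that ischemic time is settled before the drug can act for every graft, so that any version may be used. The bypass rule in Protocol 6.2 and the sequential second graft both contradict that.

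**Conclusion.** The point holds as a missed gain in precision of low severity. Ischemic time is available, relevant to the mechanism and unused in the efficacy model. Across assumed within-center correlations of 0 to 0.4 the gain at SD 137 is 0 to about 5.5 points of power for 70 mmHg and 0 to about 6.4 points for 50 mmHg. At the stated 24-hour SD of 117 it is 0 to about 3.7 and 0 to about 6.6 points. At r = 0.3 and SD 117 it is 2.1 and 3.6 points. At r of 0.1 or less it is under half a point.

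These figures assume 50 evaluable patients per arm, a linear relation, and a covariate that treatment does not affect. The last assumption is met by first-allograft cold ischemic time, or by total ischemic time closed at de-clamping. It is not assured by total ischemic time as the documents now allow it to be recorded.

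**What to change.** Before unblinding, add first-allograft ischemic time to the SAP 9.5.1 primary model as one prespecified linear covariate, with a covariate-by-time-point term so that the slope may differ at 0 and 24 hours. Choose one of two intervals:

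- cold ischemic time as SAP 5 defines it, from donor cross-clamp to removal from cold storage; or
- total ischemic time closed at vascular de-clamping of the first allograft, and never at the off-bypass time.

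If total time is chosen, first reconcile the SAP 5 definitions with Protocol 6.2 and confirm which clock time was recorded for bypass patients. Cold ischemic time avoids that step. Do not adjust for second-graft time or for bypass. Substitute the overall mean, ignoring arm, where a clock time is missing. Keep the model without the covariate as a sensitivity analysis, and record the departure from Protocol 9.4.2 in SAP 1.2.

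The cost is two degrees of freedom and a short SAP revision, with no new data. SAP 1.1 has the plan finalized before database lock and SAP 8.2 places unblinding after it, so the change can be made blind.
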